8.2.3.4 Dose adjustments in Pd arm

Dose adjustments for patients treated with pomalidomide and dexamethasone combination in the case of hematological toxicity are shown in Table 5.

Table 5 - Guidelines for dose adjustments for hematologic toxicities - pomalidomide/dexamethasone combination

Adverse event	Recommended action	
	Dexamethasone ^a	Pomalidomide
Platelets		
Thrombocytopenia Grade 3 without bleeding	
Day 1 of cycle: delay until improvement $\geq 50 \times 10^9/L$^b and administer at same dose level^c
 
Within cycle: maintain full dose of study treatment as planned
	
Thrombocytopenia Grade 4 with or without bleeding	
Day 1 of cycle: delay Day1 administration until improvement $\geq 50 \times 10^9/L$^b and administer at the same dose level^c
 
Within cycle: maintain full dose of study treatment as planned
 
Further episodes: same recommendations
	
Day 1 of cycle: delay Day 1 administration until recovery and decrease pomalidomide by one dose level^c
 
Within cycle: hold pomalidomide until bleeding is controlled and platelet recover $\geq 50 \times 10^9/L$, and then re-start with 1 dose level decrease up to planned Day 21. Next cycle will be re-started with this one dose level decrease
 
Second episode: same recommendation with decrease of pomalidomide by a second dose level
 
Third episode: discontinue pomalidomide

Adverse event	Recommended action	
	Dexamethasone ^a	Pomalidomide
Neutropenia		
Neutropenia Grade 3 (≥ 0.5 and $< 1.0 \times 10^9/L$)	Day 1 of cycle: delay until recovery $\geq 1.0 \times 10^9/L$ and administer at same dose level ^a Within cycle: maintain the same dose level as planned	
Neutropenia Grade 4 ^d ($< 0.5 \times 10^9/L$)	Day 1 of cycle: delay until recovery $\geq 1.0 \times 10^9/L$ and administer at the same dose level ^c Within cycle: maintain the same dose level as planned Further episodes: same recommendations	Day 1 of cycle: delay Day 1 administration until recovery and restart pomalidomide decreased by one dose level or consider G-CSF use and keep same dose level ^c Within cycle: hold pomalidomide until neutrophil counts recover $\geq 0.5 \times 10^9/L$ and then: - re-start with 1 dose level decrease up to planned Day 21. Next cycle will be re-started with this one dose level decrease - or consider G-CSF use and keep same dose level Second episode: same recommendations with decrease of pomalidomide by a second dose level Third episode, discontinue pomalidomide
Febrile neutropenia and/or neutropenic infection	Day 1 of cycle: delay Day 1 administration until fever and infection recover and add G-CSF until $ANC > 1 \times 10^9/L$ ^c . Then administer D1 next cycle with dexamethasone at the same dose level and pomalidomide with dose recommendations below. Within cycle: omit dexamethasone, hold pomalidomide dose and add G-CSF until fever and infection have recovered and $ANC > 1 \times 10^9/L$. Then administer dexamethasone on the planned days at the same dose level and restart pomalidomide as planned on Day 21 with the dose modifications below: When fever/infection is resolved dexamethasone re-start at same dose. For pomalidomide: 
 • First episode, resume same dose pomalidomide with G-CSF or re-start with 1 dose level decrease • Second episode, resume with action not done at first episode (same dose with G-CSF or 1 dose decrement pomalidomide) • Third episode, resume with one dose decrement of pomalidomide • Fourth episode, stop pomalidomide 	

a Patients may have dexamethasone dose omission within a cycle if certain toxicities do not recover within 3 days following the day of planned infusion (see [Section 8.2.3](#)).

b For patients with plasma cells $> 50\%$ of bone marrow nucleated cells at baseline, to initiate Cycle 2, platelet counts should be $\geq 30\,000/mm^3$ regardless response status at end of Cycle 1. During Cycles 2-4, platelet counts should be $\geq 30\,000/mm^3$, if last response is not better than SD, but if last response is PR or better during Cycles 2-4, D1 next cycle can be administered only if platelet counts $\geq 50\,000/mm^3$. For D1 administration beyond Cycle 4, platelet counts should be $\geq 50\,000/mm^3$.

c A dose delay of up to 14 days between cycles is permitted in order to recover to the patient's baseline status. Beyond 14 days, the patient must be permanently discontinued from the study (see [Section 8.2.3](#)).

d If G4 neutropenia, assess ANC every 2-3 days until $ANC \geq 0.5 \times 10^9/L$ and at least weekly thereafter until $ANC \geq 1.0 \times 10^9/L$.

Dose adjustments for patients treated with pomalidomide and dexamethasone combination in the case of non-hematological toxicity are shown in [Table 6](#).

Table 6 - Guidelines for dose adjustments for non-hematologic toxicities - pomalidomide/dexamethasone combination

Adverse event	Recommended action	
	Dexamethasone ^b	Pomalidomide
DVT/PE		
Grade 3	
Day 1 of cycle: initiate appropriate anticoagulation therapy and when efficient anticoagulation, administer cycle at the same dose level of dexamethasone and pomalidomide^a
 
Within cycle: Maintain same dose level of dexamethasone as planned. For pomalidomide:
 
 • First episode: hold pomalidomide, initiate appropriate anticoagulation therapy and restart same dose pomalidomide when efficient anticoagulation • Second episode: despite appropriate anticoagulation pomalidomide permanently discontinued 	
Grade 4	
Day 1 of cycle: delay Day 1 administration until stabilization and administer at the same dose level^a
 
Within cycle: delay dexamethasone until stabilization and resume without dose reduction at the next planned dates. If delay is >3 days omit dexamethasone until next planned administration
	Pomalidomide permanently discontinued.
Edema Grade ≥3 (limiting function and unresponsive to therapy or anasarca), excluding infusion associated reaction	Diuretics as needed, and decrease dexamethasone dose by 1 dose level; if edema persists despite above measures, decrease dose another dose level. If symptoms persist despite second reduction, dexamethasone permanently discontinued	Day 1 of cycle or within cycle : maintain same dose level of pomalidomide as planned
Allergic reaction/hypersensitivity (excluding infusion associated reaction)		
Grade 2	
Hold study treatment until < Grade 2, and patient clinically stable; then, resume study treatment at full dose^a
 
For allergic reaction related to pomalidomide, refer to site local protocol
	
Grade ≥3	Permanent discontinuation of the drug responsible for the allergic reaction.	
Infection without concomitant neutropenia	
Hold study treatment until systemic treatment of infection complete.
 
Resume all at the same dose level
	
Herpes zoster	Hold study treatment until lesions are dry, then resume all at the same dose level	
Neuropathy		
Grade 2 with pain or Grade 3	Same dose level of dexamethasone	
Hold pomalidomide until neuropathy improves to Grade ≤2 without pain.
 
First episode: resume pomalidomide with a decrease of pomalidomide by 1 dose level
 
Second episode: resume pomalidomide with a decrease by a second dose level
 
Third episode: pomalidomide permanently discontinued

Grade 4	Same dose level of dexamethasone	Pomalidomide permanently discontinued

Adverse event	Recommended action	
	Dexamethasone ^b	Pomalidomide
Confusion or mood alteration Grade ≥2 (interfering with function +/- daily activities)	Hold dexamethasone until symptoms resolve. Restart with 1 dose level reduction. If symptoms persist despite above measures, dexamethasone permanently discontinued	Day 1 of cycle or within cycle: maintain same dose level of pomalidomide as planned
Gastrointestinal dyspepsia, gastric or duodenal ulcer, gastritis		
Grade 1-2 (requiring medical management)	Treat with H2 blockers, sucralfate, or omeprazole. If symptoms persist despite above measures, decrease dexamethasone dose by 1 dose level	Day 1 of cycle or within cycle: maintain full dose pomalidomide as planned
≥ Grade 3 (requiring hospitalization or surgery)	Hold study treatment until symptoms adequately controlled. Then, restart the same dose level of pomalidomide, and decrease dexamethasone by one dose level of current dose along with concurrent therapy with H2 blockers, sucralfate, or omeprazole. If symptoms persist despite above measures, dexamethasone permanently discontinued	
Acute pancreatitis	Dexamethasone permanently discontinued Day 1 of cycle: delay Day 1 until recovery ^a and re-start the same dose level of pomalidomide Within cycle: hold all study treatment until recovery and re-start the same dose level of pomalidomide.	
Hyperglycemia ≥ Grade 3	Treatment with insulin or oral hypoglycemics as needed. If uncontrolled despite above measures, decrease dose by one dose level until levels are satisfactory	Day 1 of cycle or within cycle: maintain the same dose level of pomalidomide as planned
Muscle weakness ≥ Grade 2 (symptomatic and interfering with function +/- daily activities)	Decrease dexamethasone by one dose level. If weakness persists despite above measures decrease dose by one level. if symptoms persist dexamethasone permanently discontinued	Day 1 of cycle or within cycle: maintain same dose level of pomalidomide as planned
Renal dysfunction		
CrCl <30 mL/min	Day 1 of cycle: delay Day 1 administration until CrCl returns to ≥30 mL/min ^a Within cycle: hold study treatment until improvement to ≥30 mL/min. Then re-start the same dose level of dexamethasone and pomalidomide up to planned Day 21. If delay is >3 days omit dexamethasone.	
Any other drug related non-hematologic Grade 3-4 AE	Day 1 of cycle: delay Day 1 administration until recovery and apply same rules of dose modification than the rules below ^a Within cycle: For dexamethasone attribution omit dose if the event has not recovered within 3 days. Resume with 1 dose level decrease when toxicity has resolved to Grade 2 or less or to baseline grade. Second episode, apply new dose reduction. Third episode, dexamethasone discontinuation For pomalidomide attribution, hold dose. Resume with 1 dose level decrease when toxicity has improved to Grade 2 or less or recovered to baseline grade. Second episode, apply new dose reduction. Third episode, pomalidomide discontinuation	

^a A dose delay of up to 14 days between cycles is permitted in order to recover to the patient's baseline status. Beyond 14 days, the patient must be permanently discontinued from the study (see [Section 8.2.3](#))

^b Patients may have dexamethasone dose omission within a cycle if certain toxicities do not recover within 3 days following the day of planned infusion (see [Section 8.2.3](#))

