- Pomalidomide will be given 4 mg on Days 1 to 21 in a 28-day cycle. On Day 1 of each cycle, pomalidomide should be taken 1h to 30 min prior to isatuximab. The other infusion days of isatuximab (Day 8 and Day 15 of Cycle 1 and Day 15 of subsequent cycles), pomalidomide will be taken at the time which is the most convenient for the patient after isatuximab infusion, preferably at the same time of the previous dose.

Pd arm (control arm):

Drug administration for patients treated with pomalidomide and dexamethasone combination is as follow:

- Dexamethasone 40 mg (or 20 mg if the patient is ≥ 75 years old), PO or IV on Days 1, 8, 15 and 22.
- Pomalidomide will be given 4 mg on Days 1 to 21 in a 28-day cycle.

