Adverse event	Recommended action		
	Isatuximab ^a	Dexamethasone ^a	Pomalidomide
			Second episode: same recommendations with decrease of pomalidomide by a second dose level third episode, discontinue pomalidomide
Febrile neutropenia and/or neutropenic infection	
Day 1 of cycle: delay Day 1 administration until fever and infection recover and add G-CSF until ANC > 1 x 10⁹/L^c Then administer Day 1 next cycle with isatuximab and dexamethasone at the same dose level and pomalidomide with dose recommendations below.
 
Within cycle: omit isatuximab and dexamethasone, hold pomalidomide dose and add G-CSF until fever and infection have recovered and ANC > 1 x 10⁹/L. Then administer isatuximab and dexamethasone at the planned days at the same dose level and re-start pomalidomide up planned Day 21 with dose recommendations below:
 
 • first episode, resume same dose pomalidomide with G-CSF or re-start with 1 dose level decrease • second episode, resume with action not done at first episode (same dose with G-CSF or 1 dose decrement pomalidomide) • third episode, resume with one dose decrement of pomalidomide • fourth episode, stop pomalidomide 		

- a Patients may have isatuximab dose omission within a cycle if certain toxicities do not recover within 3 days following the day of planned infusion (see Section 8.2.3)
- b For patients with plasma cells >50% of bone marrow nucleated cells at baseline, to initiate Cycle 2, platelet counts should be ≥30 000/mm³ regardless response status at end of Cycle 1. During Cycles 2-4, platelet counts should be ≥30 000/mm³, if last response is not better than SD, but if last response is PR or better during Cycles 2-4, D1 next cycle can be administered only if platelet counts ≥50 000/mm³. For D1 administration beyond Cycle 4, platelet counts should be ≥50 000/mm³
- c A dose delay of up to 14 days between cycles is permitted in order to recover to the patient's baseline status. Beyond 14 days, the patient must be permanently discontinued from the study (see Section 8.2.3)
- d If G4 neutropenia, assess ANC every 2-3 days until ANC ≥0.5 x 10⁹/L and at least weekly thereafter until ANC ≥1.0 x 10⁹/L

Dose adjustments for patients treated with isatuximab, pomalidomide and dexamethasone combination in the case of non-hematological toxicity are shown in Table 4.

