10.1.6 Post PFS study cut-off date

Patients still on treatment at the PFS cut-off date will continue study treatment until at least 1 treatment discontinuation criterion as defined in [Section 10.3.2](#) is met. The following information will be collected during the study treatment administration:

- Study treatment administration.
- Physical examination: main diagnoses to be reported in the eCRF as AEs and newly occurring laboratory abnormalities to be recorded in laboratory pages.
- Vital signs including blood pressure, heart rate and body temperature. In addition in IPd arm, prior to start of each isatuximab infusion, 1 hour after start of each infusion and at the end of each infusion on Day 1 and on Day 15 up to and including cycle 4 and as clinically indicated.
- ECOG PS.
- Concomitant medications used throughout the cycle.
- Second primary malignancies.

- Patient diaries for oral study treatment (dexamethasone when taken orally and pomalidomide; except for study treatment doses administered by the study nurse/doctor).
- AE assessment: all related AEs and all serious AEs (regardless of relationship to study treatment) ongoing at the time of cut-off will be followed until resolution or stabilization. All new related AEs (regardless of seriousness) will be collected and followed until resolution or stabilization.

Disease assessment

- Only overall response according to assessment per Investigator and based on local laboratories and local reading of radiological assessment will be collected.
- Bone marrow aspirate (or biopsy as clinically indicated):
 - Bone marrow plasma cell infiltration (local laboratory) to confirm CR, and as clinically indicated,
 - BMA for MRD assessment in case of CR (central laboratory).

Local laboratory assessments

- In case of viral reactivation during study treatment (greater than 1 log₁₀ IU/mL increase in HBV DNA or reappearance of HBsAg or detection of HBV DNA in patients with resolved infection), ALT and AST will be closely monitored every month up to study treatment discontinuation. HBV DNA to be done as per specialist advice.

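### The Pd-arm table restarts pomalidomide on Day 21 after febrile neutropenia; the IPd table restarts it on recovery and ends on Day 21

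*Protocol*

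**What the plan says.** Both arms receive the same pomalidomide schedule (Protocol section 8.2.1): "Pomalidomide will be given 4 mg on Days 1 to 21 in a 28-day cycle".

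For febrile neutropenia or neutropenic infection arising within a cycle, the Pd arm follows Table 5 (section 8.2.3.4). The site is to "hold pomalidomide dose and add G-CSF until fever and infection have recovered", with the ANC also back above 1 × 10⁹/L. It is then to "restart pomalidomide as planned on Day 21 with the dose modifications below". A four-step list by episode follows and sets the dose: the same dose with G-CSF or one level down, then the option not yet used, then one level down, then stop.

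The IPd arm follows Table 3 (section 8.2.3.3). The hold criterion and the four-step list are the same, but the restart reads "re-start pomalidomide up planned Day 21 with dose recommendations below". The word 'to' has dropped out after 'up'; the sense is still that Day 21 is where dosing ends.

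**The concern.** The Table 5 row gives two answers to when the hold ends. The hold clause says it ends on recovery. The restart clause names Day 21, the last dosing day of the cycle. A Pd site that follows the second clause would make a recovered patient wait and then give a single dose before the rest week. An IPd site with an identical patient would resume at once.

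Pomalidomide is part of the backbone common to both arms, and the trial is meant to isolate the effect of adding isatuximab. A rule that withholds backbone drug from control patients only, after a complication that can occur in either arm, is a difference in treatment that the design does not intend. The direction is also unhelpful: any under-dosing would fall on the comparator.

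**Working it through.** The plan gives no figure to reproduce, so the check compares the text and then counts doses.

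**Rows that name Day 21 in a within-cycle pomalidomide restart**

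| Event | IPd arm (Tables 3 and 4) | Pd arm (Tables 5 and 6) |
|---|---|---|
| Grade 4 thrombocytopenia | Day 21 is the end day | "and then re-start with 1 dose level decrease up to planned Day 21" |
| Grade 4 neutropenia | Day 21 is the end day | "re-start with 1 dose level decrease up to planned Day 21" |
| Creatinine clearance <30 mL/min | Day 21 is the end day | "Then re-start the same dose level of dexamethasone and pomalidomide up to planned Day 21" |
| Febrile neutropenia or neutropenic infection | "re-start pomalidomide up planned Day 21 with dose recommendations below" | "restart pomalidomide as planned on Day 21 with the dose modifications below" |

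Seven of the eight entries use Day 21 as the end of dosing after recovery. Only the Pd febrile neutropenia entry uses it as the restart day. The protocol gives no reason for that one to differ, and none of the amendment summaries mentions this row.

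**Doses at stake in one episode**

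Inputs:
- Pomalidomide is given once daily on Days 1 to 21, so 21 doses per cycle (section 8.2.1).
- Recovery falls on day r of the cycle, with r ≤ 21. This is an assumption; the documents report no recovery times.
- Pomalidomide is resumed, which means episodes 1 to 3. At the fourth episode both tables stop the drug and the two wordings give the same result.

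Formulas:
- Restart on recovery, continue through Day 21: 21 − r + 1 = 22 − r doses.
- Restart on Day 21: 1 dose.
- Loss under the literal Table 5 wording: (22 − r) − 1 = 21 − r doses.

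| Recovery day r | Table 3 rule | Literal Table 5 | Loss | Share of the cycle's 21 doses |
|---|---|---|---|---|
| 8 | 14 | 1 | 13 | 13/21 = 61.9% |
| 15 | 7 | 1 | 6 | 6/21 = 28.6% |
| 21 | 1 | 1 | 0 | 0% |

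At the 4 mg starting dose, the r = 8 loss is 13 × 4 = 52 mg out of 21 × 4 = 84 mg for a full cycle, and the r = 15 loss is 6 × 4 = 24 mg. The loss does not carry beyond the cycle in which the episode occurs.

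**The case against.** The strongest reply is that a sensible reader would not be misled. The hold clause in the same row ends on recovery, and the episode list that follows says to resume without naming a day. The general rules in section 8.2.3.1, which cover both arms, contemplate pomalidomide being halted and restarted within a cycle and then continued. A restart on the final dosing day makes little pharmacological sense. The tables are also presented as guidelines with recommended actions. All of this supports reading the phrase as a slip, and that reading is accepted here. It does not remove the contradiction: the sentence that names the restart day names the wrong one, and a Pd site would look in this table.

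A second reply concerns consequence. The documents do not give the frequency of this event, and r = 8 is near the extreme, since onset and full recovery must both fall in the first week of a cycle. By amended protocol 07 (26-Nov-2020) few Pd patients may have remained on treatment. Under the plan's own exponential PFS with a 4-month Pd median, 0.5^(24/4) = 1.6% are progression-free at 24 months, about 2 of 150, and 0.5^(36/4) = 0.2% at 36 months, fewer than 1 of 150. These points stand and keep the matter small.

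A third reply is that the SAP would expose a systematic shortfall, because section 2.4.3.3 summarises pomalidomide cumulative dose, relative dose intensity and omissions by treatment received. That is partly right. Cumulative dose and relative dose intensity would fall. The omission count would help less, because a completed cycle with fewer than 21 doses is already flagged by the hold itself under either wording. Detecting a shortfall afterwards also does not correct the instruction.

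**Conclusion.** The concern holds. The Table 5 wording is wrong as written: it conflicts with its own hold criterion, with the matching IPd row, and with every other row that names Day 21. It is most likely a drafting error, not an intended difference between arms.

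The size is 21 − r pomalidomide doses per affected episode, from 0 at r = 21 to 13 of 21 at r = 8. It is confined to one cycle and to Pd patients who recover before Day 21 and are due to resume. The recovery days are illustrative. The documents do not show that any site followed the literal reading, and they support no estimate of an effect on PFS or on overall dose intensity.

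SAP Table 1 records that amendment 6 was issued after the primary analysis, so a change to the current text cannot alter the primary PFS comparison. The reason to correct it is patient care under section 10.1.6: "Patients still on treatment at the PFS cut-off date will continue study treatment". Any Pd patient still being treated remains subject to this row.

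**What to change.** In Table 5, febrile neutropenia and/or neutropenic infection, within cycle, replace the Day 21 restart with an instruction to restart pomalidomide once the recovery criteria are met and to continue it up to planned Day 21, at the dose set by the episode list. Under that wording a Pd patient who recovers on Day 8 receives 14 further doses instead of 1, and one who recovers on Day 15 receives 7 instead of 1, as in the IPd arm. The missing 'to' in the matching Table 3 row can be inserted at the same time as copy-editing.

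The cost is one phrase in Table 5 and one word in Table 3. No analysis, sample size or data collection changes. There is a precedent: amended protocol 4, classed as nonsubstantial, clarified the Grade 4 thrombocytopenia row of this same table. The correction can go into the next amendment.

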8.2.4 Infusion reactions

Patients should routinely receive premedications prior to isatuximab infusion as detailed in [Section 8.2.2](#) to reduce the risk and severity of IARs commonly observed with mAbs. Infusion associated reactions (for example, NCI-CTCAE version 4.03 terms “infusion related reaction”, “allergic reaction”, or “cytokine release syndrome”) are defined as AEs related to isatuximab with onset typically within 24 hours from the start of the infusion.

Patients who experience Grade 2 IAR(s) may resume isatuximab after recovery, at half of the initial infusion rate under close monitoring and supportive care as needed. Additional medication can be provided for symptom treatment as per Investigator judgment including diphenhydramine 25 mg IV (or equivalent) and methylprednisolone 100 mg IV. These patients must be informed of the potential risk of recurrent infusion associated reactions. The infusion must be completed within the time specified in the pharmacy manual.

Further treatment (subsequent isatuximab infusions) with the fixed rate:

- In case of Grade 2 IAR during the 2nd infusion, infusion could be restart at half of the initial infusion rate (25 mL/hour) when the IAR improves to Grade ≤ 1 . If symptoms do not recur after 30 minutes, the infusion rate may be increased by 50 mL/hour increments every 30 minutes, until the total volume is infused to maximum rate of 200 mL/hour.
- In case of Grade 2 IAR during third infusion and subsequent, infusion could be restarted at one-half (100 mL/hour) of the infusion rate (100 mL/hour) when the IAR improves to Grade ≤ 1 . If symptoms do not recur after 30 minutes, the infusion rate may be increased by 50 mL/hour increments every 30 minutes, until the total volume is infused to maximum rate of 200 mL/hr.

Patients with a Grade 3 or 4 isatuximab IAR must have isatuximab permanently discontinued and appropriate supportive therapy should be administered. Should an isatuximab IAR of Grade ≥ 2 occur, additional blood sampling during the AE is required for analysis of cytokine levels (TNF α , IL-1 β , IL-6, IL-4 and IFN γ), markers of complement activation (C3a, C4 and CH50) and serum tryptase, the IAR and the therapy administered must be documented in the eCRF.

Grade 3 or higher IARs must be reported as AESIs (see [Section 10.4.1.3](#)).

Table 7 - Management of infusion associated reaction

NCI-CTCAE version 4.03 criteria definition	Intervention recommendation

Mild (Grade 1)
 
Infusion interruption or intervention not indicated
	
Continuation of isatuximab infusion per the judgment of the Investigator following close direct monitoring of the patient's clinical status. Isatuximab infusion may be stopped at any time if deemed necessary. If stopped, IAR will be classified as Grade 2 as per NCI-CTCAE

Moderate (Grade 2)
 
Therapy or infusion interruption indicated but responds promptly to symptomatic treatment (eg, antihistamines, NSAIDs, narcotics, IV fluids); prophylactic medications indicated for ≤ 24 hours
	
Stop isatuximab infusion. Give additional medication with IV diphenhydramine 25 mg IV (or equivalent, see Section 8.2.2.2) and/or IV methylprednisolone 100 mg (or equivalent) as needed. Isatuximab may be resumed only after patient recovery, with slower infusion rate and with close monitoring. Blood samples for additional safety labs will be collected.
 
Important: additional blood sampling during the AE is required for analysis of cytokine levels (TNF-α, IL-4, IL-6, IL-1β, and IFN-γ), markers of complement activation (C3a, C4, CH50), serum tryptase

Severe or life-threatening (Grade 3 or 4)
 
Grade 3: prolonged (eg, not rapidly responsive to symptomatic medication and/or brief interruption of infusion); recurrence of symptoms following initial improvement; hospitalization indicated for clinical sequelae
 
Grade 4: life-threatening consequences; urgent intervention indicated
	
Stop isatuximab infusion. Give additional medication with diphenhydramine 25 mg IV (or equivalent, see Section 8.2.2.2) and/or IV methylprednisolone 100 mg (or equivalent) and/or epinephrine as needed. Blood samples for additional safety labs will be collected. Definitive treatment discontinuation.
 
Important: additional blood sampling during the AE is required for analysis of cytokine levels (TNF-α, IL-4, IL-6, IL-1β, and IFN-γ), markers of complement activation (C3a, C4, CH50), serum tryptase

Note: The infusion should be completed within the time specified in the pharmacy manual.

AE: adverse event; IAR: infusion associated reaction; IFN: interferon; IL: interleukin; IV: intravenous; NCI-CTCAE: National Cancer Institute Common Terminology Criteria for Adverse Events; NSAIDs: nonsteroidal anti-inflammatory drugs; TNF: tumor necrosis factor.

